## **4.3 Sample Size Considerations**

The sample size in this study is based on the PK assessment. The sample size of 10 adult subjects was selected to establish a PK profile of the IP. In order to allow for possible drop-outs, 11 adult subjects will be enrolled in the study.

Only after the safety of the product has been assessed and established in the adult subjects population, will 10 pediatric subjects be enrolled into the study. Assuming a 10% dropout rate, a total of 11 pediatric subjects need to be enrolled.

## **4.4 Interim Analysis**

An interim safety analysis will be performed with the adult population in order to assess the safety of FIB Grifols prior to starting enrollment of pediatric subjects. PK and efficacy interim analyses of the investigational medicinal product may also be performed in the adult population.

## 5 SUBJECT DISPOSITION

Subject disposition will be summarized by adult and pediatric populations separately and on the overall population (adult and pediatric populations combined).

Subject disposition will include the number of subjects screened, number of subjects enrolled, number and percentage of subjects in each analysis population, number and percentage of subjects completing the study.

The number and percentage of subjects discontinuing early from the study will be summarized for primary reasons of discontinuation. Also, the number and percentage of screening failures will be summarized for primary reasons of ineligibility.

Disposition status will be listed for all subjects.

## 6 PROTOCOL DEVIATIONS

Protocol deviations will be identified during the study and evaluated before the database lock. The type/category of protocol deviations and severity (i.e., minor or major) will be summarized by adult and pediatric populations and overall.

## 7 DEMOGRAPHY AND MEDICAL HISTORY

### 7.1 Demographic and Baseline Characteristics

Demographic and baseline characteristics including sex, race, ethnicity, age, age categories ( $<2$ ,  $\geq 2$  -  $<12$ ,  $\geq 12$  -  $<18$ ,  $\geq 18$  -  $<65$ ,  $\geq 65$  -  $<70$ ), baseline pregnancy test, height, weight, and body mass index will be summarized by adult and pediatric populations and overall. The congenital fibrinogen deficiency history will be summarized.

All demographic and baseline characteristics data will be listed.

### 7.2 Medical History

Medical history will be coded using the Medical Dictionary for Regulatory Activities (MedDRA) and summarized/listed by adult and pediatric populations and overall.

## 8 CONCOMITANT MEDICATION AND TREATMENT

### 8.1 Prior and Concomitant Medication

All medications as documented by the investigator will be coded using Anatomical Therapeutic Chemical (ATC) classification codes via the World Health Organization Drug classification Dictionary (WHO-DD). All medications will be summarized by adult and pediatric populations and overall and sorted alphabetically by medication class (i.e., ATC level 2) and medication sub-class (i.e., ATC level 4). If the ATC level 4 term is missing, the ATC level 3 term will be used in the medication summary table and data listing.

The following convention will be used for missing or partial end date information in order to determine whether a medication is prior or concomitant:

The unknown portions of a medication end date will be assumed to be as late as possible. If a medication end date is incomplete but the month/year of medication end date is prior to the month/year of the start of study treatment, then the medication will be considered a prior medication. If a medication end date is incomplete but the month/year of medication end date is the same as the month/year of the start of study treatment, then the medication will be considered a concomitant medication. All other incomplete medication end dates and all medications with missing end dates will be assumed to be concomitant medications. Start/end dates reported in the eCRFs will be presented in the listings.

Prior medications are defined as any medication ended prior to the start of study treatment (i.e., start of the infusion on Day 0).

Concomitant medications are defined as any medication started on or after the start of study treatment or any medication taken prior to the start of study treatment and continued after the start of study treatment during the study.

## **8.2 Extent of Study Treatment Exposure and Compliance**

The total volume infused (mL) and duration of infusion (minutes) will be summarized. Further, exposure information along with infusion interruptions will also be summarized. Duration of infusion will be calculated as stop time of infusion – start time of infusion.

Treatment compliance will be calculated as (total volume infused / total volume prepared) \* 100% during the study. The total volume prepared and dispensed by pharmacist is the intended dose volume a subject should be given based on the body weight. The treatment compliance will be listed and summarized. The number of subjects with at least 90% compliance will be calculated.

Considering different potencies from different lots are administered, the actual dose in mg/kg body weight may deviate from the planned or target dose of 70 mg/kg. The lot number, potency, actual dose infused (mg), and planned dose calculated (mg) based on the planned amount of 70 mg/kg body weight will be listed.

Additional consideration regarding treatment compliance will be given when determining legitimacy for inclusion of fibrinogen concentration data for calculation of the PK parameters. Reasons for excluding fibrinogen concentration data or a subject from the analysis of PK parameters will be documented in the CSR.

[figure not shown]
## **9 PK ANALYSIS**

PK analyses will be based on the PK population and will be performed on the adult and pediatric populations independently. PK analyses will be performed using the fibrinogen concentration values obtained by both Clauss method and antigen (ELISA) method.

## 9.1 Analysis of PK concentration and dosing data

Plasma concentrations of fibrinogen will be presented in a listing by subject, study day, date, and scheduled/nominal sampling time point. The data listing will provide details of all planned plasma collection time points relative to the start of infusion (scheduled and nominal times as shown in Section 4.1.1.1), actual collection date and clock times and actual elapsed times from the start of the infusion, as well as plasma fibrinogen concentrations. If any concentration values are excluded from the PK analyses, they will be flagged in the listing. The lot number, potency, actual dose infused (mg), and planned dose calculated (mg) based on the planned amount of 70 mg/kg body weight will also be listed. .

Plasma concentrations of fibrinogen will be summarized by adult and pediatric populations and the scheduled/nominal time point. The summaries will include n, mean, SD, 90% confidence interval (CI) for mean, coefficient of variation (%CV), median, minimum, maximum, and geometric mean.

Plasma fibrinogen concentration vs. time curves for individual subjects will be presented with the actual elapsed time from the start of the infusion plotted on the x-axis. Individual concentration vs. time plots will also be presented for all subjects on the same figure (so called spaghetti plot) for the adult and pediatric populations separately. For all subjects combined (separately for the adult and pediatric populations), mean or median plasma fibrinogen concentration vs. time curves will be presented in one figure with the nominal time (see Section 4.1.1.1) plotted on the x-axis. All plasma fibrinogen concentration vs. time curves will be plotted on both the linear and the semi-log scale.

## 9.2 Calculation of PK parameters

The PK parameters of plasma fibrinogen following single-dose administration in individual subjects will be determined as appropriate and as data permit. The PK parameters will include IVR, AUC calculated as  $AUC_{0-14\text{days}}$ ,  $AUC_{0-\infty}$ ,  $C_{\text{max}}$ ,  $t_{\text{max}}$ ,  $t_{1/2}$ , MRT, Vd, and Cl.

The PK parameters will be calculated using non-compartmental methods with WinNonlin software.

All PK parameters will be calculated using the fibrinogen concentration values obtained by both Clauss method and antigen (ELISA) method.

The pharmacokinetic parameters of interest will be determined as follows:

IVR	incremental in vivo recovery, calculated as $([FIB \text{ max (mg/dL)}] - [FIB \text{ pre-infusion (mg/dL)}]) / FIB \text{ administered (mg) / Body weight (kg)}$ , where the FIB max is the peak FIB activity during the first four hours of sampling after the end of infusion and FIB pre-infusion is the baseline FIB activity of the subject, expressed as mg/dL per
-----	---

	mg/kg. FIB administered will be the actual administered dose calculated using the actual volume administered to the subject, the potency, and the true concentration of FIB in the batch used.
AUC 0-14days	area under the concentration vs. time curve from time 0 to 14 days, calculated by a combination of linear and logarithmic trapezoidal methods and expressed in the unit of concentration × time (e.g., mg × h/dL). The linear trapezoidal method will be used for all incremental trapezoids arising from increasing concentrations and the logarithmic trapezoidal method will be used for those arising from decreasing concentrations.
AUC 0-∞*	area under the concentration vs. time curve from time 0 extrapolated to infinite time, calculated as AUC 0-t + C t /K el , where AUC 0-t is the area under the concentration vs. time curve from time 0 to the time of last quantifiable concentration (C t ), and K el is the apparent terminal first-order elimination rate constant, determined by linear regression analysis of the natural log-linear segment of the plasma concentration-time curve, expressed in time  units (1/h). At least 3 time points will be included in the determination of K el .
C max	the first observed peak plasma fibrinogen concentration following the end of drug infusion obtained directly from the experimental data without interpolation, expressed in concentration units (mg/dL).
t max	the observed time to reach peak plasma fibrinogen concentration obtained directly from the experimental data without interpolation, expressed in time units (hour).
t ½*	the terminal half-life, calculated as ln(2)/K el , expressed in time units (hour).
MRT*	mean residence time, calculated as AUMC 0-∞ /AUC 0-∞ -(TI/2), expressed in time units (hour), where AUMC 0-∞ is the area under the first moment of the concentration vs. time curve from time 0 extrapolated to infinite time, and TI is the length of infusion.*
Cl*	clearance, calculated as Dose/AUC 0-∞ , expressed in units dL/h/kg.
Vd*	volume of distribution, calculated as Cl × MRT, expressed in units dL/kg.

\*Parameters relying on the determination of the apparent terminal first-order elimination rate constant (Kel) will not be reported if R^2<0.8 or the extrapolated AUC to infinity is >20%.

Considering different potencies from different lots are administered, the actual dose amount (mg/kg) infused may deviate from the planned or target dose of 70 mg/kg. All appropriate PK parameters, such as AUC and Cmax, will be dose normalized to 70 mg/kg body weight after taking into account the actual potency. In addition, PK parameters corrected for the baseline fibrinogen level of the subject will be calculated for all the PK parameters above. The correction will be based on the fibrinogen concentration measured pre-infusion. The calculations will be the same as those described above for the un-corrected PK parameters, except the fibrinogen concentration measured pre-infusion will be deducted from the concentrations of each post-infusion sample before the calculations.

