In order to exert its hemostatic properties, fibrinogen must be present intravascularly, therefore the product is to be administered by slow intravenous infusion. The dose to be administered in the study (single-dose intravenous infusion of FIB Grifols at a dosage of 70 mg/kg of body weight) is deemed sufficient to reach the generally accepted minimum threshold for hemostasis in subjects with congenital deficiency of not less than 1g of fibrinogen per liter [6].

The usual dosage and dosage regimen of chronic replacement therapy (prophylaxis in subjects with congenital fibrinogen deficiency and bleeding tendency) with human fibrinogen has not been yet clearly established. [5]

In this study, the rate of infusion is to be controlled by means of an infusion pump. Delivery will be performed at a rate not higher than 5 mL/minute (it is acceptable to titrate up to this rate at the investigator's discretion). If an adverse event (AE) occurs during the infusion, the infusion rate may be reduced or the infusion interrupted until symptoms subside. Subsequently, the infusion may be resumed at a rate tolerated by the subject, but not exceeding 5 mL/minute. All subjects will be monitored at different time points after the infusion ends for any signs of AE.

2.5 COMPLIANCE WITH THE PROTOCOL, GOOD CLINICAL PRACTICE AND THE APPLICABLE REGULATORY REQUIREMENTS

This clinical trial will be conducted in accordance with the ethical principles that have their origins in the Declaration of Helsinki of the 18th World Medical Assembly, June 1964, and consecutive updates, in compliance with the approved protocol of the study, with any approved amendment of the protocol, in compliance with International Conference on Harmonisation Good Clinical Practices (ICH GCP, Topic E6), and in compliance with other applicable regulatory requirements.

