To date, the adequate prophylactic regimen to treat subjects with congenital deficiency and severe life-threatening bleeding tendency has not been yet clearly established and its efficacy remains controversial, although positive trends have been reported from retrospective studies and case reports.[\[6, 13, 18, 36\]](#)

Other clinical trials have studied the safety, pharmacokinetics and pharmacodynamics of fibrinogen concentrates in congenitally deficient subjects. [2, 40, 41] These studies showed a good correlation between fibrinogen levels determined by functional (Clauss) and antigen methods and confirmed previous data indicating a terminal half-life ($t_{1/2}$) of 3.0 to 5.3 days. For other PK parameters (volume of distribution [Vd], clearance [Cl], incremental in vivo recovery [IVR]), larger differences were found depending on the product used, reporting in vivo recoveries of 94% in one case and 54% in the other and 2-3 fold differences in Vd and Cl. For the same parameters, large differences (2-fold) were also found in terms of between-subject variability.

In all cases, fibrinogen capacity for restoring normal hemostasis was demonstrated by normalization of previously abnormal (prolonged) standard coagulation tests: TT, PT, and activated partial thromboplastin time (aPTT) values.

Hemostatic efficacy of treatment with fibrinogen concentrates has also been evaluated both in vitro and in vivo as well as in clinical studies in congenital and acquired fibrinogen deficiency. [42, 43, 44, 45, 46, 47, 48] Many of these studies have used pre-infusion and post-infusion rotational thromboelastometry (ROTEM) parameters, mainly maximum clot firmness (MCF) to demonstrate hemostatic efficacy. MCF is highly dependent on the concentration and activity of platelets and fibrinogen and is considered a functional marker/surrogate endpoint indicative of a subject's hemostatic competency. Many studies and papers have evaluated the correlation of thromboelastographic parameters with clinical bleeding occurrence and support the increasing use of this device for bedside monitoring of high-risk subjects in order to provide guidance for use of blood components and hemostatic products administration. [49, 50, 51, 52, 53, 54, 55, 56, 57, 58]

From these studies, as well as from years of clinical experience in the use of fibrinogen concentrates, it has been demonstrated that fibrinogen infusions were well tolerated and fibrinogen concentrates have a good safety profile.

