3. Day 1 (24 hours post-infusion): central laboratory testing only

4. Day 2 (48 hours post-infusion): central laboratory testing only (not applicable for pediatric subjects weighing <30 kg)
5. Day 4 (96 hours post-infusion): central laboratory testing only
6. Day 6 (144 hours post-infusion): central laboratory testing only
7. Day 9 (216 hours post-infusion): central laboratory testing only
8. Day 14 (336 hours post-infusion): central laboratory testing only (not applicable for pediatric subjects weighing <30 kg)

The exact time and date of taking the samples for the PK analysis will be recorded by the study staff for the PK analysis.

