5. SELECTION AND WITHDRAWAL OF SUBJECTS

5.1 SUBJECT INCLUSION CRITERIA

Subject eligibility will be based on the presence of congenital fibrinogen deficiency manifested as afibrinogenemia and the willingness to participate the study.

Subjects fulfilling the following inclusion criteria are eligible for participation in the study:

1. Male or female subjects less than 70 years old^a.
2. Sign the written ICF, or the subject's parent or legal guardian signs the ICF where applicable, and the Subject Authorization Form (SAF) where applicable. Pediatric subjects, as defined by local regulations, will be asked to sign an age appropriate assent form.
3. Subjects diagnosed with congenital fibrinogen deficiency manifested as afibrinogenemia.
4. Subjects with a fibrinogen level undetectable¹, or equal or less than 30 mg/dL determined by both Clauss and antigen methods at baseline² (sample drawn within 24 hours prior to infusion on Day 0 Visit will be tested locally) or at Screening Visit³ (sample should be drawn at least 14 days prior to infusion on Day 0 Visit to be tested at central laboratory).

¹ Limit of detection for fibrinogen level determination must be 30 mg/dL or lower for both methods.

² For sites that have the capability of performing fibrinogen level determinations locally by both Clauss and antigen methods with a limit of detection of 30 mg/dL or lower.

³ For sites that do not have the capability of performing fibrinogen level determinations by both Clauss and antigen methods locally or have methods that are not sensitive enough (limit of detection: 30 mg/dL).

5. Female subjects of child-bearing potential^b must have a negative test for pregnancy blood or urine HCG-based assay at baseline (sample drawn within 24 hours prior to infusion on Day 0 Visit)
6. Female subjects of child-bearing potential^b and their partner have agreed to practice contraception using a method of proven reliability (ie, hormonal methods, barrier methods, intrauterine devices methods) to prevent a pregnancy during the course of the clinical trial
7. Subjects must be willing to comply with all aspects of the clinical trial protocol, including blood sampling, for the whole duration of the study

^aThe enrollment of pediatric subjects (below 18 years of age) will be initiated only after the safety of FIB Grifols in the adult subjects has been evaluated by the sponsor.

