8.2.4 LABORATORY PANELS

Laboratory tests will include:

1. Serum clinical chemistry: including creatinine, BUN, ALT, AST, ALP, LDH, TB, glucose, sodium, potassium, chloride and calcium.

2. Hematological parameters: CBC, including platelet count and differential leukocyte count.
3. Markers of activation of coagulation: different measures indicative of activation in the coagulation pathway (D-dimer, ATIII, TAT, F₁₊₂).

Blood specimens for laboratory tests will be collected at different time points throughout the study. Laboratory tests results will be collected in the corresponding CRF/eCRF entry. Abnormal (out of range) results will be flagged by the reporting laboratory. The investigator will be required to indicate the clinical relevance of out of range (abnormal) results. Laboratory results out of the normal range judged by the investigator as clinically relevant will be considered AEs.

In the case of markers of activation of coagulation, their relationship with plasma fibrinogen levels pre- and post-infusion will be studied.

In case of pediatric sampling, pediatric tubes would be provided to reduce the amount of blood drawn for lab works, including the complete elimination of virology, immunogenicity, and markers of activation of coagulation lab works. Pediatric subjects will not undergo Month 3 virology and immunogenicity follow-up visits, and their participation in the study will finish at the Week 4 Visit. Pediatric subjects weighing less than 30 kg will also have an even more reduced blood sampling schedule as detailed in [Table 4-4](#) and [Table 4-5](#):

- Day 0 - baseline (including the retention sample)
- Day 0 - 1 hour post-infusion
- Day 0 - 8 hours post-infusion
- Day 1 - 24 hours post-infusion
- Day 4 - 96 hours post-infusion
- Day 6 - 144 hours post-infusion and
- Day 9 - 216 hours post-infusion

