#### **4.1.1.3 Plasma Concentration Missing Values**

For PK analysis, any invalid plasma concentration values of fibrinogen will be treated as missing. If necessary, invalid or missing values will be interpolated or extrapolated using PK principle, as appropriate, and such interpolations or extrapolations will be documented in the CSR.

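### Children under 30 kg have no fibrinogen sample after Day 9; if the LLOQ is low, the SAP's 20% extrapolation rule withholds half-lives above about 3.9 days and may shorten the pediatric mean

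*SAP*

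**What the plan says.** - **Reporting rule.** SAP 9.2 extrapolates AUC from the last quantifiable concentration, with Kel fitted to at least three points. A footnote withholds every Kel-dependent parameter (AUC0-∞, t½, MRT, Cl, Vd) if R² is below 0.8 "or the extrapolated AUC to infinity is >20" percent. One limit serves all subjects.
- **Sampling.** Protocol 4.6.1.6 lists "Day 14 (336 hours post-infusion): central laboratory testing only (not applicable for pediatric subjects weighing <30 kg". Protocol 8.2.4 says "Pediatric subjects weighing less than 30 kg will also have an even more reduced blood sampling schedule", and its list ends at Day 9 (216 h). The SAP does not mention this reduced schedule; its pediatric nominal-time table (4.1.1.1) runs to Day 14 without exception.
- **Expected half-life.** Protocol 2.7 cites terminal half-lives "of 3.0 to 5.3 days" from studies of other concentrates.
- **Assay limit.** SAP 4.1.1.2 generally sets values below the LLOQ to zero but gives no LLOQ. The only assay figure is an eligibility requirement in Protocol 5.1: "Limit of detection for fibrinogen level determination must be 30 mg/dL or lower for both methods".
- **Gaps.** SAP 4.1.1.3 says that, if necessary, "invalid or missing values will be interpolated or extrapolated using PK principle".
- **Summaries.** SAP 9.3 summarises adults and children separately, and children by age group if the data allow. Nothing is split by weight or schedule.
- **Role of PK.** SAP 4.3: "The sample size in this study is based on the PK assessment".

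**The concern.** A limit on extrapolated AUC is a usual safeguard when everyone is sampled for the same length of time. Here the lightest children are followed five days less, and whether a child passes depends on the half-life itself: a slow eliminator still has much of the curve ahead at Day 9, a fast one does not. The reported values are then a sample selected on the quantity being estimated. The pediatric mean half-life would read short and mean clearance high. Because adults are sampled to Day 14, part of any apparent difference between adults and children could come from the schedule. Separately, the Day 9 to 14 part of AUC0-14days is never observed in these children.

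**Working it through.** The plan states no half-life cut-off, so there is no document figure to reproduce.

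**1. Cut-off.** Under mono-exponential decline the extrapolated share is (Ct/Kel)/AUC0-∞ = Ct/C0 = 2^(-T/t½), where T is the time of the last quantifiable sample and C0 the post-infusion level. It equals 0.20 at t½ = T/log2(5), with log2(5) = 2.322.

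- T = 9 d: 9/2.322 = 3.88 d (3.87 d with the SAP's trapezoid on the under-30-kg schedule and a 0.5 h infusion).
- T = 14 d: 14/2.322 = 6.03 d.

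| t½ (d) | Extrapolated, last sample Day 9 | Last sample Day 14 |
|---|---|---|
| 3.0 | 12.5% | 3.9% |
| 3.5 | 16.8% | 6.2% |
| 4.0 | 21.0% | 8.8% |
| 4.5 | 25.0% | 11.6% |
| 5.3 | 30.8% | 16.0% |

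If a fast phase holds a share f of AUC, the Day 9 cut-off is 9/log2((1-f)/0.2): 4.00, 4.15 and 4.50 d for f = 0.05, 0.10 and 0.20. All lie inside 3.0-5.3 d.

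**2. LLOQ condition.** At t½ = 3.876 d the Day 14 level is 2^(-14/3.876) = 0.082 of C0. The full schedule therefore keeps every half-life in 3.0-5.3 d only while the LLOQ is at most about 8% of C0. Protocol 2.4 expects "not less than 1g of fibrinogen per liter", that is 100 mg/dL. Taking C0 as 100-150 mg/dL (upper end assumed), 8% is 8-12 mg/dL. Share of half-lives reported, uniform on 3.0-5.3 d, noise-free:

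| LLOQ/C0 | Full schedule | Under 30 kg |
|---|---|---|
| 0.08 | 100% | 38% |
| 0.10 | 85% | 38% |
| 0.12 | 70% | 38% |
| 0.15 | 34% | 26% |
| 0.16 | 21% | 21% |
| 0.20 | 0% | 0% |

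The last row follows directly: any quantifiable Ct is then at least 0.20 of C0.

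**3. Effect on the pediatric mean.** Assumptions: low LLOQ, half-lives uniform on 3.0-5.3 d (mean 4.15 d), lognormal assay error with CV 0-15%, three-point terminal fit, SAP trapezoid and both reporting limits. Subjects were simulated on each schedule and drawn in 40,000 sets of ten.

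| Children under 30 kg, of 10 | Shift in mean t½ | Half-lives reported |
|---|---|---|
| 0 | about 0% | about 10 |
| 2 | -1.4% to -2.4% | 8.5-8.8 |
| 4 | -3.3% to -5.1% | 7.5-7.6 |
| 6 | -6% to -9% | 6.3-6.4 |
| 8 | -10% to -14% | 5.0-5.3 |
| 10 | -17% to -22% | 3.8-4.3 |

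Within the under-30-kg group at 10-15% error, the mean is 3.24-3.35 d under the rule and 4.27-4.31 d if every fit with R² of at least 0.8 is kept. With constant Vd and no noise, mean Cl among the reported values in this group is 1.18 times the mean for all of the group.

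**4. Other half-life distributions** (lognormal, CV 15-25%, noise-free, under-30-kg group only). Mean 3.0 d: 4-12% withheld, shift -1% to -7%. Mean 3.5 d: 22-29%, -6% to -13%. Mean 4.15 d: 56-65%, -15% to -22%.

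**5. AUC0-14days.** The unobserved Day 9-14 share is (2^(-9/t½) - 2^(-14/t½))/(1 - 2^(-14/t½)). This is 0.086/0.961 = 8.9% at 3.0 d and 0.148/0.840 = 17.6% at 5.3 d.

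**The case against.** The effect needs three things that the documents do not give for this product: a low LLOQ, an appreciable number of children under 30 kg, and half-lives often above 3.9 d. If the LLOQ were near the 30 mg/dL eligibility limit, both schedules would report almost nothing (0-7% at C0 of 100-150 mg/dL and 10% error), which is general loss rather than selective loss. The uniform distribution is assumed, and a fast phase raises the cut-off. PK is descriptive. With ten children and SD 2.3/√12 = 0.66 d, the planned 90% CI half-width is 1.833 × 0.66/√10 = 0.38 d, about 9% of the mean, so the shift stays within it for up to six light children. Reported n, concentration listings and study-report notes would reveal the loss, age-group summaries may partly separate light from heavy children, and the SAP bases the sample size on 10 adults, who are sampled to Day 14. The rule also screens out weak estimates: 20-32% of the half-lives it withholds from light children would be off by more than 25% (5-15% with a four-point fit).

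These points limit the size and priority of the issue, and the conditions stand. They do not remove the selection. Counts and listings show that values are missing but do not correct the mean, and a Day 14 value extrapolated from the same Kel adds no information. A group with no light children is also not the likeliest case. The dose volume is 70 × 0.05 = 3.5 mL/kg (Protocol 4.5.4.1), the rate is capped at 5 mL/min, and the SAP gives a mean pediatric infusion of 0.5 h. The mean volume is then at most about 150 mL, and the mean weight at most about 150/3.5 = 43 kg, allowing for rounding of the 0.5 h.

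**Conclusion.** The concern holds, as a conditional point of modest weight. The cut-off of about 3.9 d (up to about 4.5 d with a fast phase), against 6.0 d with a Day 14 sample, follows from the schedule and the rule alone and falls inside the half-life range the protocol cites. Selective loss requires an LLOQ below roughly 16% of the post-infusion level and is fullest at 8% or less. From 20%, the rule leaves no Kel-dependent parameter for anyone under mono-exponential decline. Given a low LLOQ and the uniform assumption, the pediatric mean half-life reads about 1-5% short with two to four light children of ten, and 17-22% short if all are light. The harm is confined to the Kel-dependent pediatric summaries; Cmax, tmax and IVR are outside the rule, and no test depends on it.

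**What to change.** In SAP 9.2 and 9.3:

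1. Keep the 20% rule for the main summary if wished, but calculate and list all Kel-dependent parameters that have at least three points and R² of at least 0.8. Flag those above 20% and show the percent extrapolated.
2. Summarise t½, AUC0-∞, MRT, Cl and Vd with and without the flagged values (mean and median), and give the number flagged by weight group (under 30 kg, 30 kg and over).
3. Add AUC from 0 to 216 h for all subjects as the exposure measure that every schedule observes, and label AUC0-14days in children under 30 kg as extrapolated.
4. State the LLOQ of both assays beside the rule.

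The cost is SAP wording, one extra summary and one partial AUC from data already collected; no new samples are needed. The drawback is precision: flagged half-lives rest on a 96-216 h window, five days or about one half-life, so they belong in the sensitivity summary and not unmarked in the main mean. In the simulation, keeping all fits with R² of at least 0.8 moved the ten-child mean by only +1% to +4%.

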## **12 CHANGES IN PLANNED ANALYSIS IN PROTOCOL**

The evaluation of at least 90% of the planned dose was administered for the PP population will use the prepared volume per the pharmacy manual as the reference. The reason is that different potencies from different lots are administered, the actual dose in mg/kg body weight may deviate from the planned or target dose of 70 mg/kg automatically.

Incremental IVR will be calculated for fibrinogen levels from the peak level recorded within and including the first four hours after the end of infusion and reported as [mg/dL]/[mg/kg], not just the first hour. Based on preliminary data review of the fibrinogen levels, it seems that

$C_{max}$  occurs between 1 and 2 hours after the end of infusion, later than the previously planned 1 hour. So in order to ensure the  $C_{max}$  was captured the time duration is extended. Also, for RiaSTAP™, a fibrinogen concentrate (human), the incremental IVR was determined from fibrinogen levels obtained up to 4 hours post-infusion and we want to match that.

PK parameters corrected for the baseline fibrinogen level of the subject will be calculated, in addition to the uncorrected PK parameters as planned.

All appropriate PK parameters, such as AUC and  $C_{max}$ , will be dose normalized to 70 mg/kg body weight after taking into account the actual potency.

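### Read as written, the supplementary baseline-corrected IVR in SAP 9.2 deducts the pre-infusion fibrinogen level twice; the planned IVR is unaffected

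*SAP*

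**What the plan says.** SAP 9.2 sets out the PK parameters and how each is calculated. IVR comes first: "The PK parameters will include IVR, AUC calculated as" and so on through the list. Its numerator is the highest fibrinogen level in the four hours after the end of infusion minus the pre-infusion level, where "FIB pre-infusion is the baseline FIB activity of the subject". The result is expressed in mg/dL per mg/kg given. Protocol 4.1 and SAP 3.1 define it in the same way.

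The last paragraph of SAP 9.2 adds a second set of results: "PK parameters corrected for the baseline fibrinogen level of the subject will be calculated for all the PK parameters above". It fixes the method in two parts. First, "The calculations will be the same as those described above for the un-corrected PK parameters". Second, the one departure is that "the fibrinogen concentration measured pre-infusion will be deducted from the concentrations of each post-infusion sample before the calculations".

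SAP 12 lists this as an addition to the protocol's analysis: "PK parameters corrected for the baseline fibrinogen level of the subject will be calculated, in addition to the uncorrected PK parameters as planned". Neither section exempts IVR.

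**The concern.** Most of the listed parameters (the AUCs, peak concentration, half-life, residence time, clearance, volume) are computed from the raw concentration profile. Deducting the baseline first gives them a meaningful corrected version. IVR differs because its definition is already a rise over baseline. If the baseline is removed from the peak sample and the formula then subtracts it again, the result is no longer a recovery.

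Two IVR figures would then exist for each assay and age group. The one labelled as corrected for baseline would be the wrong one, and it would be wrong in one direction only. IVR is a named PK endpoint and the trial is sized on PK, so an incorrect second value under that label should not reach the study report.

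**Working it through.** The plan gives no expected IVR, so there is no figure of its own to reproduce. The check is algebra on the SAP 9.2 definitions.

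**Inputs**
- P: peak within four hours after the end of infusion (SAP 9.2). It is a post-infusion sample, so the correction applies to it.
- B: pre-infusion level (SAP 9.2). It is not a post-infusion sample, so the correction leaves it unchanged in the formula.
- D: dose per kg, taken as the planned 70 mg/kg. I read the denominator of the IVR formula as mg per kg, in line with its stated unit.
- Range of B: 0 to 30 mg/dL. The upper end is the entry limit in inclusion criterion 4 (Protocol 5.1).
- Rise R = P − B: **assumed**, 70 to 165 mg/dL, because the documents give no expected value.

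**Step 1. Un-corrected IVR, as defined**

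IVR = (P − B)/D = R/D

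**Step 2. Corrected IVR, following the last paragraph of SAP 9.2**

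Replace P by P − B, keep the formula and leave B as it is:

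IVR(corrected) = ((P − B) − B)/D = (P − 2B)/D

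**Step 3. Error**

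Absolute: (P − 2B)/D − (P − B)/D = −B/D

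Relative: −B/(P − B) = −B/R

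**Step 4. Numbers at D = 70 mg/kg**

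| B (mg/dL) | Error −B/70 | Relative, R = 70 | Relative, R = 100 | Relative, R = 165 |
|---|---|---|---|---|
| 0 | 0 | 0% | 0% | 0% |
| 5 | −0.07 | −7% | −5% | −3% |
| 10 | −0.14 | −14% | −10% | −6% |
| 20 | −0.29 | −29% | −20% | −12% |
| 30 | −0.43 | −43% | −30% | −18% |

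Worked example: with R = 100 and B = 30, P = 130. The un-corrected IVR is 100/70 = 1.43. The corrected IVR as written is (130 − 60)/70 = 1.00.

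**Step 5. When the error vanishes**

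SAP 4.1.1.2 generally sets values below the quantification limit to zero. Then B = 0 and the two versions agree. If another imputation is used, as that section allows, the error is the imputed value divided by 70.

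**Step 6. After the fix**

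With IVR left out of the correction, or with baseline deducted only once, the value is (P − B)/D. That is identical to the planned IVR: 1.43 in the example.

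**The case against.** The best defence is that this is loose drafting and no competent PK analyst would follow it literally. The same blanket scope takes in time to peak, which cannot change when a constant is subtracted. SAP 9.2 also opens by saying that parameters will be determined as appropriate. In a baseline-subtracted profile the pre-infusion value is naturally zero, and an analyst who treated it so would recover the correct IVR. This has some force, but the SAP does not say to reset that value. In the same paragraph dose normalisation is confined to appropriate parameters, whereas baseline correction is not. SAP 9.3 does write an exception for time to peak when geometric means are planned. Even on the generous reading, the corrected IVR merely duplicates the planned one under a label suggesting that it differs. The same phrase cures both readings.

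The second defence concerns size, and it largely stands. Subjects have afibrinogenemia and must have had no fibrinogen product for 21 days. With the half-life of 3.0 to 5.3 days given in Protocol 2.7, 21 days is 21/5.3 = 4.0 to 21/3.0 = 7.0 half-lives, leaving about 6% to 1% of an earlier dose. If that dose had raised fibrinogen by 70 to 165 mg/dL (assumed, as above), between about 0.5 mg/dL (70 × 0.8%) and 11 mg/dL (165 × 6.4%) would remain. Endogenous traces could add to this. Baselines of 20 or 30 mg/dL are therefore limit cases.

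A reader might also infer that a comparison with a licensed concentrate is at risk, because SAP 12 refers to matching one. What SAP 12 matches is the four-hour sampling window for the peak. No comparison of IVR values is planned.

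**Conclusion.** The rule as written gives a wrong result for one supplementary output. The corrected IVR is too low by baseline/(dose per kg) in each subject with a quantifiable pre-infusion level, by either assay: 0.07 at 5 mg/dL, 0.14 at 10 mg/dL and 0.43 (mg/dL)/(mg/kg) at 30 mg/dL, assuming 70 mg/kg. At 30 mg/dL the relative error is −18% to −43% over the assumed rises of 165 to 70 mg/dL.

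Three stronger readings are not supported:
- *That the trial's IVR endpoint is biased.* The IVR defined in Protocol 4.1, SAP 3.1 and SAP 9.2 subtracts baseline once, and SAP 12 keeps the un-corrected set. No hypothesis test or sample-size figure uses the corrected IVR.
- *That every subject, or the group mean, is materially affected.* The error is zero where baseline is set to zero. Neither the quantification limit nor the share of subjects below it is given, so the effect on means cannot be computed and may be nil.
- *That 0.43 is a ceiling.* The 30 mg/dL limit applies to the eligibility sample, tested locally or at screening. The PK baseline is normally a separate central-laboratory sample (Protocol 4.6.1.6), and the actual mg/kg may differ from 70.

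**What to change.** In the last paragraph of SAP 9.2, directly after "PK parameters corrected for the baseline fibrinogen level of the subject will be calculated for all the PK parameters above", add: *except incremental IVR, which is already baseline-corrected by definition*. Report IVR once per assay in each age group. SAP 12 describes the correction without claiming that it covers every parameter, so it needs no separate exception once 9.2 is clear.

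The cost is one phrase and no corrected-IVR output to produce. Data collection, subjects and the other corrected parameters are unaffected.
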